### **Adverse events**

AEs will be coded using the latest version of Medical Dictionary for Regulatory Activities (MedDRA) available prior to clinical database lock.

Any information collected (e.g. relatedness to study drug, action taken etc.) will be listed.

The following adverse event summaries will be produced by treatment arm:

- Adverse events (overall and severe), regardless of study drug relationship by primary system organ class and preferred term
- Adverse events (overall and severe), with suspected study drug relationship by primary system organ class and by preferred term
- Serious adverse events (overall and severe), regardless of study drug relationship, by primary system organ class and preferred term
- Serious adverse events (overall and severe), with suspected study drug relationship, by primary system organ class and preferred term
- Adverse events leading to study drug discontinuation (overall and severe), regardless of study drug relationship, by primary system organ class and preferred term
- Adverse events requiring dose adjustment or study-drug interruption (overall and severe), regardless of study drug relationship, by primary system organ class and preferred term
- Adverse events requiring additional therapy (overall and severe), regardless of study drug relationship, by primary system organ class and preferred term
- Deaths (all and on-treatment) by primary system organ class and preferred term (Safety Set 3 and 4 only).

AEs will be summarized by presenting the number and percentage of patients having at least one AE, and having at least one AE by system organ class and/or preferred, severity and relation to study drug by treatment arm. A patient with multiple occurrences of an AE will be counted only once in the AE category.

An overall summary of type of AEs (e.g. serious, leading to study drug discontinuation, requiring dose adjustment or/and interruption) will be presented by severity and treatment arm.

All AEs will be listed. Any information collected (e.g. regardless to study drug, action taken etc.) will be listed as well as the duration of the AE. The listings of all deaths, serious adverse events, adverse events leading to study drug discontinuation, and adverse events requiring dose adjustment or interruption will also be provided.

### **Adverse events of special interest**

Specific groupings of AESI will be considered and the number of patients with at least one event in each grouping will be reported. Note that certain adverse events may be reported within multiple groupings.

All AESI groupings are defined through the use of Preferred Terms (PT), High Level Terms (HLT), System Organ Classes (SOC), Standardized MedDRA Queries (SMQ), Novartis MedDRA Queries (NMQ) or through a combination of these components. All AESI definitions or AE groupings are specified in the electronic Case Retrieval Strategy (eCRS). The latest version of the eCRS available at the time of the analysis will be used.

AESI will be summarized by grouping, preferred term and treatment arm (specifying severity, SAE, relationship, leading to treatment discontinuation, leading to dose adjustment/interruption and requiring additional therapy).

### **Laboratory data**

Laboratory data from all sources (central and local laboratories) will be combined. All laboratory values will be converted into International System (SI) units.

Raw values as well as absolute and relative change from baseline values for hematology, biochemistry and urinalysis laboratory parameters will be summarized descriptively per time window and treatment arm on the Safety Set 3 and 4 (see [Table 4-2](#) for time windows definition).

Shift tables based on normal ranges to compare baseline to the worst post-baseline value will be provided by parameter and treatment arm for hematology, biochemistry and urinary laboratory data. Same shift table will be provided based on notable/extended ranges for key safety laboratory parameters defined in [Table 4-2](#).

**Table 2-4      Definition of notable/extended ranges for key safety laboratory parameters**

Laboratory parameters	Criteria for notable/extended ranges
Platelet count	< 100 x 10  /L (extended range <50 x 10  /L)
Absolute neutrophils	< 1.5 x 10  /L (extended range <0.5 x 10  /L)
Serum creatinine	> 33% increase from baseline and > ULN at two consecutive measurements at least 7 days apart
Recalculated creatinine clearance	<60 mL/min at two consecutive measurements at least 7 days apart (extended range <40 mL/min at two consecutive measurements at least 7 days apart)

Urinary protein/urinary creatinine ratio	> 1.0 (mg/mg) at two consecutive measurements at least 7 days apart
ALT/AST	>5 x ULN and 2 x baseline (extended range >10×ULN and >2×baseline value)

Recalculated creatinine clearance will be calculated using the Schwartz formula (for pediatric population at baseline) described in [Section 4.6.3](#). The Modification of Diet in Renal Disease (MDRD) derivation will be provided in the derived datasets only for possible future requests.

A listing of all laboratory values with values flagged to show the corresponding range classifications relative to the laboratory reference ranges will be provided by laboratory data and treatment arm. Assessment day relative to first dose of study drug will be included and all laboratory assessments collected outside of the on-treatment period will be flagged.

A listing of patients with laboratory abnormalities based on normal ranges and notable/extended ranges will also be provided.

Normal ranges by laboratory parameter will also be provided in a separate listing.

## Vital signs, weight and body mass index

The following criteria define clinically notable abnormalities for vital signs and weight values:

**Table 2-5** Definition of clinically notable abnormalities for vital signs and weight values

Parameter 	Weight	High	Increase from baseline $\geq 10\%$
		Low	Decrease from baseline $\geq 10\%$
Pulse rate (beats per minute)	High 	12-18 months	> 140
		18-24 months	> 135
		2-3 years	> 128
		3-4 years	> 123
		4-6 years	> 117
		6-8 years	> 111
		8-12 years	> 103
		12-15 years	> 96
		15-18 years	> 92
	Low 	12-18 months	< 103
		18-24 months	< 98
		2-3 years	< 92
		3-4 years	< 86
		4-6 years	< 81
		6-8 years	< 74
		8-12 years	< 67
		12-15 years	< 62
		15-18 years	< 58

Systolic and diastolic blood pressure will be listed individually.

Descriptive statistics will be tabulated per time window and treatment arm using absolute change from baseline values for each vital sign measure, weight and BMI (see [Table 4-2](#) for time windows definition) separately for Safety Set 3 and 4.

All vital sign assessments, weight and BMI will be listed by treatment arm, patient and parameter. In the listings, clinically notable values will also be flagged.

### **Cardiac evaluations**

Cardiac evaluations include ECG and echocardiogram. Any abnormalities at baseline will be summarized as described in [Section 2.3](#). All findings of patients with new or worsened abnormalities since baseline will be listed separately for Safety Set 3 and Safety Set 4.

### **Ocular evaluations**

The number of patients with available assessment for each type of ocular evaluation and eye side will be provided by treatment group.

#### **Visual acuity**

Visual acuity will be measured using the Snellen visual acuity. This is determined by establishing the smallest optotypes that can be identified correctly by the patient at a given observation distance. Snellen visual acuity can be reported as a Snellen fraction (m/M) in which the numerator (m) indicates the test distance and the denominator (M) indicates the distance at which the gap of the equivalent Landolt ring subtends 1 minute of arc. The following formula for conversion from Snellen acuity results to the logMAR score (Holladay 1997) will be applied and the LogMAR score will be calculated for each timepoint.

$$\text{logMAR score} = -\log_{10}(m/M).$$

LogMAR scores will be categorized as follows: <0.1, ≥0.1 to <0.2, ≥0.2 to <0.3, ≥0.3 to <0.6, ≥0.6. Shift tables using these categories to compare baseline to increases and decreases from baseline of logMAR score will be presented at each visit, for each eye side by treatment group in the core phase. Number and percentage of patients with worst change from baseline for each logMAR category will be summarized by treatment arm. Changes from baseline at each visit will be calculated for assessments done in the same condition (with/without correction) as at baseline. The shift tables and summaries will be repeated for the safety set 4.

A listing with the Snellen fraction and logMAR score will be provided for all patients with a flag for patients who have 0.2 or more increase in the post-baseline logMAR score.

#### **Slit lamp**

For each considered evaluation type and eye, the number of patients with and without abnormality (normal, insignificant, significant and any) will be provided by treatment arm. In addition, a shift table will present any changes in interpretation compared to baseline. A listing of patients with any abnormality will be provided.

### Tonometry

The number of patients with clinically relevant post-baseline value of less than or equal to 5 mmHg and changes from baseline intraocular pressure above 5 mmHg and 10 mmHg will be summarized by treatment arm. For patients with such values, a listing will also be provided. Intraocular pressure will also be summarized in shift tables (baseline and post baseline value at each time point) for each eye side considering the following categories:  $\leq 5$ ,  $> 5$  to  $\leq 21$ ,  $> 21$  to  $\leq 30$  and  $> 30$  mmHg.

### Fundus oculi

For each eye, the number of patients with and without abnormality (normal, insignificant, significant and any) will be provided by treatment arm. In addition, shift table will be done to present any changes in interpretation compared to baseline. A listing of patients with any abnormality will be provided.

### Growth and Development

**Growth velocity** will be listed at baseline and core EOT visit and summarized using descriptive statistics by sex and age group during the core phase for the Safety Set 3. Summaries and listing will be repeated for the entire granule period on the Safety Set 4.

The growth velocity in height which evaluates the rate of growth per year will be calculated on the difference with the previous measure of height (in cm) and the time period (in days) as:

Growth velocity (cm / year) =

$$\frac{(height V_x - height V_{x-1}) * F}{date V_x - date V_{x-1}}$$

(with  $V_x$  = actual visit ;  $V_{x-1}$  = previous visit ;  $F = 365.25$ ).

**Pubertal stage** assesses the stage of physical development of sex characteristics. The characteristics breast development, pubic hair, testes and penis size are evaluated based on the Tanner scale: for each characteristic there are 5 classes (Tanner stage 1 to 5) indicating the level of development of that specific characteristic.

The age will be summarized descriptively at baseline and core EOT visit for the core phase by sex, characteristic, Tanner stage and treatment arm. For the entire granule period, the same summary will be repeated at baseline and at each annual assessment (core phase and extension phase displayed separately).

**A listing will be provided** including the Tanner stage as well as the individual records for each sex characteristic by visit. Patients with delayed puberty will be flagged in the listing. Delayed puberty in boys is defined as failure to attain Tanner Stage 2 (for both testis and pubic hair) by age 14 (Crowley and Pitteloud 2012) and in girls is defined as the failure to attain Tanner Stage 2 (for both breast development and pubic hair) by age 13, or absence of menarche by age 15 or absence of menarche within 5 years of attainment of Tanner Stage 2 (Fenichel 2012).

### Other safety data

All data from auditory evaluation, hepatitis testing, and pregnancy test will be listed.

Patients with clinically significant abnormal interpretations or abnormal values will be flagged as well as positive pregnancy test results.

Data related to blood transfusion during treatment phase will be listed by treatment arm.

## 2.9.7 Pharmacokinetics parameters

### 2.9.7.1 Pharmacokinetics analyses

The assessment of pharmacokinetic parameters was characterized in the primary CSR and will not be repeated for the EoC CSR. For details on this analysis, refer to the primary analysis SAP.

In the EoC CSR, all individual PK concentration data will be listed on the FAS-3.

### 2.9.7.2 Exploration of PK/PD relationship

The exposure-efficacy relationship was characterized in the primary CSR and will not be repeated for the EoC CSR since no additional data was collected for these endpoints after the primary CSR data cut-off. For details on this analysis, refer to the primary analysis SAP.

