## Amendment 6 (24-Jun-2021)

### Amendment rationale

As of 24-Jun-2021, 67 patients are ongoing in the extension phase of the study. All patients had completed the Core phase of the study by 18-Dec-2018. The primary analysis for this study was completed on 07-Dec-2018 (data cut-off date 31-May-2018).

The main purpose of this amendment is to introduce the requirement for central collection and assessment of photographs from ocular examinations (lens photographs and wide angle fundus photographs) collected during the study by a Novartis designated imaging Contract Research Organization (CRO). This change is in response to a Health Authority request to submit CALYPSO ophthalmic data (for up to 2 years of follow up) to support the ocular safety evaluation of deferasirox.

Clarification was also added to state that for patients who need correction, the best corrected visual acuity should be tested when performing the distance visual acuity test and that the corrected visual acuity should be documented in the source records.

In addition, mitigation procedures have been implemented throughout the protocol to ensure participant safety and trial integrity during a Public Health emergency, as declared by Local or Regional authorities i.e. pandemic, epidemic or natural disaster.

Finally, assessment of the study Risk/Benefit in light of the ongoing coronavirus disease 2019 (COVID-19) pandemic at the time of this protocol amendment concluded that there are no additional risks related to COVID-19 for this study. Patient with cytopenias are more susceptible to infections in general, compared to patients without cytopenias. There have been postmarketing reports of cytopenias in patients treated with deferasirox and patients with cytopenias may be at higher risk of COVID-19 with a poorer prognosis. The periodic monitoring of blood counts and interruption of study treatment in patients who develop unexplained cytopenia, as defined in the protocol, are expected to mitigate this risk.

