**Figure 4-1**      **Study schema**

## **4.2 Timing of interim analyses and design adaptations**

One interim analysis has been added to allow for early analysis of the data if requested by the health authority. All the analyses included in the interim analysis will be descriptive. The IA will be performed by the Novartis study team. No decisions regarding the future course of the trial is anticipated at the time of the IA and the trial will continue.

All patients randomized in the study and who have completed a minimum of 12 weeks of treatment exposure or discontinued from treatment core phase at the time of the cut-off date will be included in the interim analysis (Section 10.7).

The cut-off for the primary analysis will be 24 weeks after approximately 96 ICT naive patients have been randomized.

The core data analysis is planned when all patients have completed their 48 week study treatment in the core phase including safety follow-up (if applicable).

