## **1 Introduction**

This document details the planned statistical analysis for data collected during the core and extension phases in the study CICL670F2202. The SAP from the primary analysis (CSR SAP Amendment 3, dated 26Mar2018) will be used as a reference for this SAP. The CSR SAP is located at the following CREDI location:

Clinical Study Report (CSR) deliverables (tables, figures, listings - TFLs) and further programming specifications are described in separate documents namely TFL Shells and Programming Datasets Specifications (PDS), respectively. An interim and the primary analysis were performed in the study. The data cut-off date for the interim analysis was 16-Nov-2017 and included all randomized ICT naïve patients who had completed a minimum of 12 weeks of treatment exposure or discontinued from the treatment core phase by the cut-off date. The primary analysis was performed when 96 randomized ICT naïve patients had completed 24 weeks of treatment or discontinued early (data cut-off date: 31-May-2018). All data collected within the core phase of the study at the time of the primary data cut-off date were reported in the primary analysis CSR.

This analysis plan describes the analyses for an End of Core Phase (EoC) CSR requested by the CHMP that will include the cumulative data from the completed core phase and extension phase with a data cut-off date of 18-Jan-2021. This data cut-off date allows the inclusion of all patients who have completed a minimum of 3 years of treatment or discontinued from treatment in the core or extension phase. Only the analyses based on the core and extension phase described in this analysis plan will be performed for this EoC phase CSR. Analyses that were presented in the primary CSR and for which no additional data was collected after the primary analysis data cut-off date (e.g. baseline demographics) will not be repeated for the EoC phase analysis.

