To evaluate compliance using a daily PRO/ObsRO questionnaire	Rate of dosing instructions deviations (doses missed / not taken at the same time every day)	Yes
To evaluate pre-dose PK data to support the assessment of compliance	Pre-dose deferasirox concentrations in all patients [except Egypt] at weeks 1, 3, 5, 9, 13, 17, 21, 25, 29, 33, 37, 41 and 45 (13 samples)	No
Post-dose data to be analyzed along with pre-dose PK data	Post-dose deferasirox concentrations between 2 and 4 hours post-dose at Weeks 5 and 9 (2 samples)	No
To explore exposure-response relationships for measures of safety and effectiveness	Serum creatinine change from baseline, notable serum creatinine events, serum creatinine clearance change from baseline and notable serum creatinine clearance	No

Objective	Endpoint	To be reported in EoC CSR	
	events, urine protein creatinine ratio change from baseline and serum ferritin change from baseline, in relationship to pre- and post-dose deferasirox concentrations.		
Secondary (Optional Extension phase)	To assess additional safety data about new formulation (granules) in pediatric population	Overall safety, as measured by frequency and severity of adverse events (including active monitoring for renal toxicity; including renal failure, hepatic toxicity; including hepatic failure, and gastrointestinal hemorrhage), and changes in laboratory values from baseline (serum creatinine, creatinine clearance, ALT, AST, RBC and WBC). In addition, vital signs, physical, ophthalmological, audiometric, and growth and development evaluations will be assessed.	Yes

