To evaluate compliance using a daily PRO/ObsRO questionnaire	Rate of dosing instructions deviations (doses missed / not taken at the same time every day)	No (presented in EoC CSR, no extension data)
To evaluate pre-dose PK data to support the assessment of compliance	Pre-dose deferasirox concentrations in all patients [except Egypt] at weeks 1, 3, 5, 9, 13, 17, 21, 25, 29, 33, 37, 41 and 45 (13 samples)	No (presented in EoC CSR, no extension data)

Objective	Endpoint	To be reported in final CSR
Post-dose data to be analyzed along with pre-dose PK data	Post-dose deferasirox concentrations between 2 and 4 hours post-dose at Weeks 5 and 9 (2 samples)	No (presented in EoC CSR, no extension data)
To explore exposure-response relationships for measures of safety and effectiveness	Serum creatinine change from baseline, notable serum creatinine events, serum creatinine clearance change from baseline and notable serum creatinine clearance events, urine protein creatinine ratio change from baseline and serum ferritin change from baseline, in relationship to pre- and post-dose deferasirox concentrations.	No (presented in EoC CSR, no extension data)
Secondary (Optional Extension phase)		
To assess additional safety data about new formulation (granules) in pediatric population	Overall safety, as measured by frequency and severity of adverse events (including active monitoring for renal toxicity; including renal failure, hepatic toxicity; including hepatic failure, and gastrointestinal hemorrhage), and changes in laboratory values from baseline (serum creatinine, creatinine clearance, ALT, AST, RBC and WBC). In addition, vital signs, physical, ophthalmological, audiometric, and growth and development evaluations will be assessed.	Yes

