## 2.9 PD and PK/PD analyses

The exposure-efficacy relationship was characterized in the primary CSR and will not be repeated for the final CSR since no additional data was collected for these endpoints after the primary CSR data cut-off. For details on this analysis, refer to the primary analysis SAP.

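### The End-of-Core and final SAPs leave the trough-compliance and PK/PD models on data cut at 31-May-2018, and the reason given for PK/PD conflicts with the trial's own dates

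*SAP*

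**What the plan says.** The analyses at issue are specified in the primary SAP (Amendment 3). Section 2.9.3.2 models troughs to support the assessment of compliance, 2.9.3.3 summarises PAS-1 concentrations, and 2.9.3.4 fits the PK/PD models. Section 2.1 of that SAP excludes everything collected after the cut-off. The EoC SAP introduction dates the cut-off: "The primary analysis was performed when 96 randomized ICT naïve patients had completed 24 weeks of treatment or discontinued early (data cut-off date: 31-May-2018".

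The two later plans then say the following.

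- **EoC SAP 2.9.7.2**, on the exposure-efficacy relationship: it "will not be repeated for the EoC CSR since no additional data was collected for these endpoints after the primary CSR data cut-off".
- **EoC SAP 2.9.7.1**: "The assessment of pharmacokinetic parameters was characterized in the primary CSR and will not be repeated for the EoC CSR". Individual concentrations are to be listed on FAS-3.
- **EoC SAP Table 1-1**: No for the pre-dose, post-dose and exposure-response objectives. The pre-dose endpoint is defined there as "Pre-dose deferasirox concentrations in all patients [except Egypt] at weeks 1, 3, 5, 9, 13, 17, 21, 25, 29, 33, 37, 41 and 45".
- **Final SAP Table 1-1**, same three objectives: "No (presented in EoC CSR, no extension data").
- **Final SAP 2.8 and 2.9**: these point to the primary report instead, and 2.9 gives the reason that "no additional data was collected for these endpoints after the primary CSR data cut-off".

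Both later SAPs state a general rule. The EoC introduction drops an analysis if it was in the primary report and has gained no data since. Final SAP sections 1 and 1.2 allow a repeat where there are additional data.

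**The concern.** The primary cut-off was tied to week 24 of the naive cohort, not to the end of the core phase. Protocol 4.2 sets it out: "The cut-off for the primary analysis will be 24 weeks after approximately 96 ICT naive patients have been randomized". The same section plans a core data analysis once everyone has completed 48 weeks. Later-enrolled naive patients therefore still had up to five of their 13 scheduled troughs ahead of them at the cut-off, with the ferritin and renal values that pair with those troughs.

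If those samples were collected, the reason in EoC 2.9.7.2 and final 2.9 is wrong, and the general rule points to repeating the analyses. The cross-references make it worse: the EoC plan defers to the primary report, and the final SAP's table defers to an EoC report that was never due to contain these results.

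Two secondary objectives are at stake: pre-dose PK in support of compliance, and exposure-response. Protocol 2.2 acknowledges that pill counts overestimate adherence and uses pre-dose PK as a direct supporting measure. EoC Table 1-1 records that the primary objective was not met, so readers will look to this supporting evidence. The missing part is the second half of treatment in the naive patients, who are the primary population.

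**Working it through.** **Inputs**
- Cut-off 31-May-2018 (EoC SAP introduction), set 24 weeks after about the 96th naive randomization (Protocol 4.2).
- Core completion: "All patients had completed the Core phase of the study by 18-Dec-2018" (Protocol Amendment 6 rationale).
- Troughs at weeks 1, 3, 5, 9, 13, 17, 21, 25, 29, 33, 37, 41 and 45; post-dose samples at weeks 5 and 9 (Protocol Table 3-1 and 7.2.5.1.1).
- Ferritin, creatinine and urine protein/creatinine ratio to core end of treatment (Protocol 7.2.2, 7.2.4.6.2 and 7.2.4.6.3).
- Randomized by 15-Jun-2017: 60 naive and 118 pre-treated, with pre-treated accrual complete (Amendment 4 rationale). By 06-Dec-2017: 94 naive and 116 pre-treated, 210 in all (Amendment 5 rationale).

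**1. Timeline.**
- 31-May-2018 minus 168 days = 14-Dec-2017, the implied 96th naive randomization.
- Plus 336 days (week 49) = 15-Nov-2018. Plus 30 days of follow-up = 15-Dec-2018, or 22-Dec-2018 with the 7-day visit window. The stated 18-Dec-2018 fits.
- Cut-off to 18-Dec-2018 is 201 days.
- The last scheduled trough (week 45) falls about 18 to 28-Oct-2018 if 18-Dec-2018 includes the 30-day follow-up, or on 20-Nov-2018 if that date is a week 49 visit.

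**2. Who has troughs after the cut-off.** Visit date = randomization + (week − 1) × 7 days. A given trough falls after 31-May-2018 if randomization came after:

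| Trough | Randomized after |
|---|---|
| Week 29 | 16-Nov-2017 |
| Week 33 | 19-Oct-2017 |
| Week 37 | 21-Sep-2017 |
| Week 41 | 24-Aug-2017 |
| Week 45 | 27-Jul-2017 |

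A pre-treated patient randomized as late as 15-Jun-2017 reached week 45 on 19-Apr-2018, before the cut-off. The loss therefore falls on naive patients.

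**3. How many.** Naive accrual between the two dated counts is 94 − 60 = 34 over 174 days, plus 2 to reach 96. Assume uniform accrual (34/174 = 0.195 per day) and place the last 2 at 14-Dec-2017. Patients missing each trough = 0.195 × (days from the threshold date to 06-Dec-2017) + 2:
- Week 29: 20 days, 5.9
- Week 33: 48 days, 11.4
- Week 37: 76 days, 16.9
- Week 41: 104 days, 22.3
- Week 45: 132 days, 27.8

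The total is about 84. Placing whole patients at even spacing gives 28 patients and 83 troughs. Extremes: if all 34 enrolled on 15-Jun-2017, 2 × 5 = 10 troughs; if all enrolled on 06-Dec-2017, 36 × 5 = 180.

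**4. As a share.** The models use PAS-1, Safety Set 3 and FAS-3, so all patients count: 210 + 2 = 212.

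| Denominator | Scheduled troughs | 83 left out | 10 to 180 left out |
|---|---|---|---|
| Naive, weeks 29-45 | 96 × 5 = 480 | 17% | 2% to 37.5% |
| All, weeks 29-45 | 212 × 5 = 1,060 | 8% | 1% to 17% |
| All, all weeks | 212 × 13 = 2,756 | 3% | 0.4% to 6.5% |

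**5. What gained no data.** A week 9 post-dose sample falls after the cut-off only for someone randomized after 05-Apr-2018. Core completion by 18-Dec-2018 rules that out for anyone completing 48 weeks. PAS-2 parameters come from patients enrolled under the original protocol, at weeks 1 and 5, so nothing new arose there either.

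**The case against.** Several stronger readings are tempting, and the documents do not support them.

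- *All three PK objectives are truncated.* Post-dose PK and the PAS-2 parameters gained nothing after the cut-off, so omitting them is sound.
- *The no-new-data reason is given for all PK work.* It is written only under PK/PD, in a sentence that names exposure-efficacy. It reaches trough-compliance only through the general rule in the EoC introduction.
- *PK collection ran to December 2018.* The last scheduled trough was in October or November.
- *The data are never used.* The EoC SAP lists all concentrations (2.9.7.1), summarises ferritin to week 48 (2.9.3) and summarises laboratory data by window (2.9.6). What is missing is the trough modelling and summaries, and the PK/PD models.
- *One arm is favoured.* Calendar truncation under 1:1 stratified randomization gives no evident mechanism for bias between arms. The cost is late-treatment information.

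A benign reading also deserves an answer. Primary SAP 2.9.3.4 names pre-dose and post-dose concentrations together as covariates. If both had to enter one model, only weeks 5 and 9 would contribute and no new model data would exist. But Protocol 10.5.6.3 fits ferritin on pre-dose concentrations alone and treats the two separately for the renal endpoints, and the trough-compliance model in 2.9.3.2 needs no post-dose sample.

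Finally, the final SAP's general clause could permit a repeat. Its own Table 1-1 and section 2.9 then say it will not happen, and its section 2 narrows the exception to significant data changes affecting reported results.

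**Conclusion.** The point holds in limited form. For pre-dose PK and its matched ferritin and renal values, the claim that nothing further was collected conflicts with the sampling schedule, the cut-off rule and the core completion date. Final SAP Table 1-1 is also wrong to place these results in the EoC report. As a result no plan runs the PAS-1 trough-compliance model or the PK/PD models on the completed core phase, contrary to the plans' own rule for omitting analyses.

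The size is modest overall: about 83 troughs from about 28 naive patients, which is 3% of all scheduled troughs. It is concentrated in late treatment, at 8% of all week 29-45 troughs and 17% of those in naive patients. The 17% should not be read as the loss to the models, which use all patients. These are counts of scheduled visits. They rest on uniform accrual between the two dated counts and a last naive randomization on 14-Dec-2017. They ignore dropout, the Egyptian patients (no PK samples) and the PAS-1 evaluability rules.

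No hypothesis test or success claim depends on these outputs. The severity is moderate, because the defect is an incorrect statement about data completeness together with secondary and exploratory analyses left on truncated data.

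**What to change.** 1. Delete the no-additional-data statements in EoC SAP 2.9.7.2 and final SAP 2.9.
2. Correct the final SAP Table 1-1 rows that place the PK and PK/PD results in the EoC report.
3. Set the pre-dose PK-compliance and exposure-response rows to Yes, in the final SAP if the EoC report is closed. Leave the post-dose row and the PAS-2 parameters as not repeated, citing the primary report.
4. Re-run primary SAP 2.9.3.2, the PAS-1 pre-dose summaries in 2.9.3.3 and the models in 2.9.3.4 on the completed core phase. Report how many troughs after 31-May-2018 are added, by arm and by naive or pre-treated status.
5. Label the primary-report versions as based on incomplete core data.

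If the sponsor decides not to re-run, the SAP should give the true reason and the number of samples left out. The cost is SAP wording and a re-run of existing programs on data already collected; no new samples are needed.
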